6.11.3 Vital Signs

Vital signs will be collected at screening, prior to start of Period 1 treatment (Treatment A), on the day of first TDS application/first dose within study period, and weekly thereafter (i.e., on Days 1, 8, 15, 29, and 36 within study period). Additionally, vital signs will be collected in the event of premature study termination. Vital signs include the following endpoints:

- Systolic blood pressure (mmHg)
- Diastolic blood pressure (mmHg)

Page 35 of 61 Confidential

- Pulse rate (bpm)
- Respiration rate (breath/min)
- Oral temperature (C)

Descriptive statistics will be presented for observed values and changes from baseline by treatment at the following time points for subjects in the Safety Analysis Population:

- Screening,
- Baseline (last available measurement prior to start of Period 1 treatment),
- Day of first TDS application (Treatments A and B)/first dose (Treatment C) within study period)
- Days 1, 8, 15, 22, 29, and 36 within study period
- Early Termination (last available on-treatment vital signs collected for subjects who prematurely terminate from the study)

All vital signs data will be listed.

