- 1. ECG: A 12-lead ECG will be obtained after the subject has been in the supine position for at least 3 minutes. Abnormal ECGs may be repeated for confirmation in which case only the repeated ECG will be recorded. The QT interval corrected for heart rate will be calculated with Fridericia's formula (QTcF). Vital sign measurements will be obtained after the subject has been seated for at least 3 minutes. Vital signs will include sitting blood pressure (systolic and diastolic measurements), pulse rate (beats per minute), respiratory rate (breaths per minute), and oral temperature.
- 2. Vital signs will be collected prior to the first dose/application of each treatment period and weekly thereafter. Temperature checks may be permitted daily.
- 3. Hematology, Serum Chemistry, Coagulation Panel, and Urinalysis: Laboratory safety tests will be obtained at the Screening visit, Day -1, Day 36, Day 72, Day 109, and at the Early Termination visit.
- 4. COVID-19 Testing: Subjects must have an inactive COVID-19 test at Screening and Day -1. COVID-19 testing will occur weekly while subjects are housed in the clinic. Additional test may be conducted at the discretion of the Principle Investigator in consultation with the Medical Monitor.
- 5. C-SSRS Columbia-Suicide Severity Rating Scale Assessments will be performed at Screening, Day -1, Day 37, Day 72, Day 109, and the Early Termination visit.
- 6. Drug Administration:

In Period 1, all subjects will wear patches (Treatment A). In Periods 2 and 3, subjects will either wear patches (Treatment B) or receive once-per-day oral Aricept (Treatment C). There is a treatment-free day on Day 36 of each period.

In each period wherein the treatment consists of a patch, the subjects will wear a total of 5 patches for a total of 35 days (5 weeks). The last (5th) patch in the period will be removed after the morning blood draw on Day 36 (168 hour time point after the last patch in the period). No treatment will be administered on Day 36 of the period.

In each period (Period 2 or 3) wherein the treatment consists of oral Aricept, the subjects will take an oral dose daily for a total of 35 days (5 weeks). The last oral dose in the period will be administered on the morning of Day 35. No treatment will be administered on Day 36 in each period.

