With regard to the pharmacokinetics of donepezil after  $Corplex^{TM}$  Donepezil TDS application, of note is Study P-15086 wherein bioequivalence was demonstrated between the registration batch of the CorplexTM Donepezil TDS (TDS A) and oral Aricept®. The mean steady state donepezil plasma concentration-time profiles after weekly donepezil TDS application (TDS A, 10 mg/day) and daily oral 10 mg/day Aricept are shown in Figure 1. In accordance with the long donepezil half-life of approximately 70 hours, steady state was reached by Day 29, at the beginning of Week 5 during which the steady state exposure was evaluated. In line with the intension of the TDS application to also decrease the peak-to-through fluctuations of plasma donepezil concentrations, a lower donepezil Cmax after the TDS application was observed compared to daily oral Aricept dosing. The mean steady-state donepezil concentrations after TDS application fell between the steady-state Cmax and Cmin after daily oral Aricept administration at most time points.

Corium has made changes to the intended commercial manufacturing process including changes to increase the bond strength between the active layer and the overlay portion of the patch. Since these and other changes may be considered major differences compared to the process used for the clinical batch used in Study P-15086, the purpose of the current study is to demonstrate bioequivalence at steady state between the highest strength (10 mg/day) TDS manufactured with the new manufacturing process and oral 10 mg/day Aricept®.

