#### 9.4.5. End of Treatment (Day 109)

The end of the treatment phases of the study is Day 109. After all procedures during the Treatment Phase are conducted including the collection of the 168-hour blood sample after the last dose of study drug, the following End-of-Treatment procedures will be conducted:

- 1. Complete physical examination.
- 2. Body weight.
- 3. Clinical laboratory tests (chemistry, hematology, coagulation, and urinalysis). Samples for clinical laboratory tests at the end of treatment can be collected under non-fasted conditions.
- 4. Urine pregnancy test (females only).
- 5. Vital signs after a minimum of 3 minutes of rest (respiratory rate, pulse rate, blood pressure, oral temperature).
- 6. 12-lead ECG will be obtained after the subject has been in the supine position for at least 3 minutes.
- 7. Assessment of the Columbia Suicide Severity Rating Scale (C-SSRS), "Since Last Visit" version. If a subject has a clinically significant suicidal ideation based on the C-SSRS assessment, in the opinion of the Investigator, further evaluation and/or preventive intervention steps for suicidal behavior will be taken, at the discretion of the Investigator.
- 8. Review of concomitant medications, treatment and/or therapies.
- 9. Assessment of adverse events.

Subjects will be discharged from the research clinic when the Investigator determines that the subjects are medically stable, and all end-of-treatment procedures are completed.

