#### 12.4. Vital Signs

Vital sign measurements will be obtained after the subject has been seated for 3 minutes. Vital signs will include sitting blood pressure (systolic and diastolic measurements), pulse rate (beats per minute), respiratory rate (breaths per minute), and oral temperature. In order to ensure accuracy, out-of-range vital signs may be repeated once, at least 2 minutes after an abnormal finding.

Vital signs will be collected at prior to the first dose/application and weekly thereafter. Temperature checks may be permitted daily.

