6.2.2 Baseline

For variables that will be summarized by treatment, the baseline for each period is defined as the last non-missing value (either scheduled, unscheduled or repeat) that is collected before dosing, in the relevant period.

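### The by-treatment vital-sign table shows a pre-dose reading under the 10 mg TDS and Aricept as a change from a pre-Period-1 baseline, in conflict with the SAP's period-specific baseline

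*SAP*

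**What the plan says.** SAP 6.11.3 states: "Descriptive statistics will be presented for observed values and changes from baseline by treatment at the following time points". The list that follows includes:

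- "Baseline (last available measurement prior to start of Period 1 treatment", the only baseline this section names;
- "Day of first TDS application (Treatments A and B)/first dose (Treatment C) within study period";
- Days 1, 8, 15, 22, 29 and 36 within the study period, so the first day appears twice.

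The SAP places the first-day reading only on the day of first application or dose. The protocol fixes the time. Footnote 2 of its Schedule of Events says "Vital signs will be collected prior to the first dose/application of each treatment period and weekly thereafter", and Section 12.4 agrees: "Vital signs will be collected at prior to the first dose/application and weekly thereafter".

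SAP 6.2.2 has another baseline rule: "For variables that will be summarized by treatment, the baseline for each period is defined as the last non-missing value" collected before dosing in that period.

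Protocol 6.1 plans no washout between periods. A patch comes off on the morning of Day 36, the last tablet is taken on the morning of Day 35, and the next treatment starts on Study Day 37 or 73. Protocol Section 3 refers to the "long donepezil half-life of approximately 70 hours".

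At Study Day 109, Protocol 9.4.5 collects a further set: "Vital signs after a minimum of 3 minutes of rest (respiratory rate, pulse rate, blood pressure, oral temperature"). SAP 6.11.3 does not list that day.

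**The concern.** Every subject starts Treatment B or C soon after another donepezil treatment. The pre-dose reading on the first day of Period 2 or 3 therefore reflects the treatment just stopped. Expressed as a change from the drug-free baseline before Period 1 and printed in the column of the treatment about to start, it shows a change under B or C before either has been given in that period. Under Treatment A the same row is zero, because the pre-dose reading is itself the baseline. A reader comparing columns could take the 5 mg TDS as having no effect on the first day, and the 10 mg TDS and Aricept as having an immediate one.

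The adverse-event rule in SAP 6.11.1 works the other way: an event belongs to the treatment received immediately before its onset. An event starting on the morning of Study Day 37 before dosing goes to Treatment A, while a pulse reading at that moment is printed under B or C. Vital signs are a named safety endpoint (SAP 3.3), so two attribution rules in one safety report should not stand.

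**Working it through.** The documents state no figure on this point, so there is none to reproduce. The check traces the timing and then estimates how much of the previous drug is present.

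**Timing.** Patch removal on Day 36 to the next start on Day 37 is 24 h. Last tablet on Day 35 to the next start is 48 h. Each first-day reading then falls as follows:

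| Printed under | Sequence and period | Preceding treatment | Scheduled gap |
|---|---|---|---|
| A | both, Period 1 | none | not applicable |
| B | ABC, Period 2 | A (5 mg TDS) | 24 h |
| B | ACB, Period 3 | C (Aricept) | 48 h |
| C | ACB, Period 2 | A (5 mg TDS) | 24 h |
| C | ABC, Period 3 | B (10 mg TDS) | 24 h |

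**Residual drug.** Fraction remaining = 2^(−hours / half-life). The half-life of 70 h is the protocol's; 60-80 h is an assumed range. Decline is taken as mono-exponential, with no further absorption after patch removal.

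- 24 h after a patch: 2^(−24/70) = 0.788, about 79% (76-81%).
- 48 h after a tablet: 2^(−48/70) = 0.622, about 62% (57-66%).

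SAP Section 1 allows for continued absorption after patch removal, which would raise the patch figure.

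**Gap before Period 3.** A footnote to Listing 16.2.4.6 in the SAP addendum says visits marked as extension days indicate a gap of 7-8 days between the end of Period 2 (its Day 36) and the start of Period 3. Where that applies, at a half-life of 70 h:

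- after a patch, 168-192 h: 0.189 to 0.149, about 19-15%;
- after tablets, 192-216 h: 0.149 to 0.118, about 15-12%.

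The Period 2 readings are unaffected and stay at about 79%.

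**Illustration with assumed effects.** Suppose pulse falls 2 bpm on the 5 mg TDS and 4 bpm on either 10 mg treatment, in proportion to level, with equal sequence sizes. None of these effects is in the documents. The first-day changes from the pre-Period-1 baseline are then:

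- A: 0.
- B: −(0.788 × 2 + 0.622 × 4) / 2 = −2.0 bpm.
- C: −(0.788 × 2 + 0.788 × 4) / 2 = −2.4 bpm.
- B with the gap: −(1.576 + 0.149 × 4) / 2 to −(1.576 + 0.118 × 4) / 2 = −1.1 to −1.0 bpm.
- C with the gap: −(1.576 + 0.189 × 4) / 2 to −(1.576 + 0.149 × 4) / 2 = −1.2 to −1.1 bpm.

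**The two baselines.** Under 6.11.3 the row shows a change inherited from the preceding treatment. Under 6.2.2 the same reading is normally the period baseline, so its change is zero for A, B and C alike. The result in this row depends on which section the programmer follows.

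**The case against.** The best defence is SAP 6.2.2. It covers variables summarised by treatment, which vital signs are. Under it the first-day row is a reference value and nothing is credited to B or C. That is correct as far as it goes, and it rules out one inference a reader might draw, that the row is uninformative whichever baseline is used: under 6.2.2 it is the reference for every later change in the period. But 6.11.3 names its own baseline for this table, and nothing says which section prevails.

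Other limits stand:

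- A reader might infer that the end-of-treatment reading is lost. It is not. Day 36 is listed within each study period, and Protocol 9.4 and 9.4.3 schedule vital signs on patch-removal days.
- A reader might apply 79% to every B and C value. It does not fit readings after tablets (62% as scheduled), nor Period 3 readings taken after the 7-8 day gap.
- The addendum records changes to the title and visit labels of Table 14.3.6.1. The shell is not shown, so the row may already be labelled as pre-dose. The current text of 6.11.3 nevertheless keeps the row.
- This is a descriptive table with no test or decision rule, and all vital signs are also listed by subject.

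**Conclusion.** The point holds for the table as SAP 6.11.3 specifies it. The first-day row and its duplicate under Treatments B and C would show a change that arose on the preceding treatment, while Treatment A shows zero by construction. The root fault is the unreconciled baseline in 6.11.3 and 6.2.2, combined with listing a pre-dose reading among the treatment's time points.

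The preceding drug is substantially present at the reading: about 79% after a patch and 62% after tablets as scheduled, and about 12-19% in Period 3 where the gap occurred. These figures rest on the 70 h half-life, mono-exponential decline and the gap counted from Day 36; the number of subjects with the gap is not given. The size of any vital-sign effect is unknown, since the documents give none.

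The consequence is a misleading row in a descriptive safety table. Bioequivalence conclusions are untouched. It is still worth correcting, because vital signs are a named endpoint and every reading needed is already collected.

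**What to change.** In SAP 6.11.3 and the specification of Table 14.3.6.1:

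1. Label the Period Day 1 reading as pre-dose, period baseline. Do not present it as a post-dose result of B or C, and start the post-dose rows at Day 8.
2. Reconcile 6.11.3 with 6.2.2 and state one baseline rule, or show changes from both baselines under separate labels.
3. Delete the duplicate row for the day of first application or dose.
4. Add the collected Study Day 109 vital signs as a separately labelled end-of-treatment/discharge reading.

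Do not pool the Period 3 pre-dose readings as a Day 37 value of the preceding treatment. With the gap, some would fall about a week after Day 36 and would not be comparable with readings taken 24 h after it.

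The cost is a wording change and minor reprogramming of one table. No new data are needed.

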6.11.4 Electrocardiogram Data

Twelve-lead electrocardiograms (ECGs) will be obtained at screening, prior to start of Period 1 treatment (Treatment A), and at the end of treatment (Day 109). Additionally, ECGs will be obtained in the event of premature study termination. Descriptive statistics for observed values and changes from baseline in the following ECG variables will be tabulated overall at the end of treatment (Study Day 109):

- Heart rate (bpm)
- PR interval (ms)
- RR interval (ms)
- QRS duration (ms)
- QT interval (ms)
- QTcB interval (ms) [Bazett's formula]
- QTcF interval (ms) [Fridericia's formula]

If an ECG measurement was repeated, only the repeated measurement was recorded.

Shift tables in relation to the overall interpretation (Normal, Abnormal NCS, and Abnormal CS) from baseline to end of treatment (Study Day 109) will be presented.

All ECG data, including details of any abnormalities, will be listed.

Page 36 of 61 Confidential

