## 5.3. Safety Objective

To evaluate the safety and tolerability, including local skin tolerability (Dermal Response and Other Effects) of once-weekly Corplex™ Donepezil TDS.

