# 9.6. Follow-Up Visit

Subjects who complete the Treatment Phase will return in  $5 \pm 2$  days after the administration of the last dose of study drug for the Follow-Up Visit.

The following procedures will be completed during the Follow-Up Visit:

- 1. Complete physical examination.
- 2. Vital signs after a minimum of 3 minutes of rest (respiratory rate, pulse rate, blood pressure, and oral temperature).

- 3. 12-lead ECG after the subject has been supine at least 3 minutes.
- 4. If applicable, perform skin irritation/tolerability assessments.
- 5. Review of concomitant medications, treatment and/or therapies.
- 6. Assessment of adverse events.

The Follow-Up Visit is the EOS for subjects who will undergo the Follow-Up procedures.

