#### 12.5. 12-Lead Electrocardiogram

A 12-lead electrocardiogram (ECG) will be obtained after the subject has been in a supine position for a minimum of 3 minutes. Abnormal ECGs may be repeated for confirmation in which case only

the repeated ECG will be recorded. The QT interval corrected for heart rate will be calculated with Fridericia's formula (QTcF).

ECGs will be obtained at Screening, Day -1, ET and EOS visit.

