6.11 Safety Analyses

The safety analyses will be presented by the treatment received for the Safety Population.

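### The Day 109 ECG summary pools subjects finishing oral Aricept with subjects finishing the 10 mg TDS, so it cannot attribute a change to patch or tablet

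*SAP*

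**What the plan says.** SAP 6.11.4 sets the ECG time points: "Twelve-lead electrocardiograms (ECGs) will be obtained at screening, prior to start of Period 1 treatment (Treatment A), and at the end of treatment (Day 109", with further ECGs at early termination. For the summary it says "changes from baseline in the following ECG variables will be tabulated overall at the end of treatment (Study Day 109". It also plans a shift table of the three-category interpretation from baseline to Day 109, with no split by treatment or sequence. It adds: "All ECG data, including details of any abnormalities, will be listed".

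The parent section, SAP 6.11, states the general rule: "The safety analyses will be presented by the treatment received for the Safety Population". SAP 6.11.2 and 6.11.3 follow it, presenting laboratory data and vital signs by treatment.

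Tables 14.3.7.9 and 14.3.7.10 name end of treatment and early termination together in their titles. SAP 6.2.3, however, groups early-termination assessments with Follow-Up as the end-of-study visit.

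In the protocol, section 9.4.5 includes the Day 109 ECG. Section 9.6 lists another at Follow-Up: "12-lead ECG after the subject has been supine at least 3 minutes". Section 12.5 says "ECGs will be obtained at Screening, Day -1, ET and EOS visit". The safety objective in section 5.3 is "To evaluate the safety and tolerability, including local skin tolerability (Dermal Response and Other Effects) of once-weekly" donepezil TDS.

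**The concern.** Day 109 is the only scheduled post-baseline ECG during confinement. None is scheduled at the end of Period 1 (Day 36) or Period 2 (Day 72), although laboratory tests are done on both days. The single ECG table therefore carries nearly all of the summarised ECG evidence on a product whose safety is a stated objective.

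Two groups contribute to that table, and they have just ended different treatments. A single overall column mixes a possible patch effect with a possible tablet effect. A reader of the study report could not tell which treatment a shift in PR or QTcF came from, and a patch-only change would look smaller than it is.

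**Working it through.** **1. The plan's own figure.** The documents give no ECG figure. The number of subjects at Day 109 rests on the 48 planned completers (Protocol 17.2, SAP 4). That figure reproduces. With a CV of 29%, the within-subject SD on the log scale is √ln(1 + 0.29²) = 0.284, and the standard error is 0.284 × √(2/48) = 0.058. Two one-sided 5% tests against 0.80–1.25, with a true ratio of 1.05 and 46 df, give 90.4% power, against the stated minimum of 90%.

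**2. What each group received before the Day 109 ECG** (Protocol Treatment Phase Schematic and 8.1).

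| Sequence | Period 3 treatment | Last drug contact | Approximate gap to Day 109 |
|---|---|---|---|
| ABC | Oral Aricept | Last tablet, Day 107 | 48 h |
| ACB | 10 mg TDS | Patch off, Day 108 | 24 h |

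The gaps assume a morning ECG; no clock time is given. The Period 2 treatment ended no later than Day 72, which is 37 days or 888 h earlier. With the half-life of about 70 h (Protocol 3), that is 888/70 = 12.7 half-lives, leaving 0.5^12.7, about 0.015%. In terms of drug level, the Day 109 ECG belongs to Period 3.

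**3. What pooling does.** The overall mean change is (n_B·d_B + n_C·d_C)/(n_B + n_C), where B is the TDS and C is Aricept. Take an illustrative 5 ms change on the TDS and none on Aricept:

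- 24:24 gives 5 × 24/48 = 2.5 ms
- 20:28 gives 5 × 20/48 = 2.1 ms
- 28:20 gives 5 × 28/48 = 2.9 ms

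At 24:24, changes of 5 and 0, 2.5 and 2.5, or 0 and 5 ms all print as 2.5 ms. The effect is diluted but not removed. What is lost is attribution.

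**4. Timing difference between the groups.** Under simple decay, 0.5^(24/70) = 0.79 of the level at patch removal remains in ACB. In ABC, 0.5^(48/70) = 0.62 of the level at the last tablet remains. This ignores continued absorption after patch removal, which SAP 1 treats as possible, and absorption of the last tablet.

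**5. Precision of a split table.** Assume an SD of the ECG change of 10, 15 or 20 ms (not in the documents) and 24 subjects per column.

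- The 95% half-width for one column is t(23) × SD/√24 = 4.2, 6.3 or 8.4 ms.
- For the difference between columns it is t(46) × SD × √(2/24) = 5.8, 8.7 or 11.6 ms.

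**6. ECG schedule side by side.**

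- Protocol Schedule of Events: Screening, Day -1, Period 3 discharge, early termination. Follow-Up is not marked.
- Protocol 9.4.5 and 9.6: Day 109 and Follow-Up.
- Protocol 12.5: Screening, Day -1, early termination and end of study. Section 9.7 defines end of study as Follow-Up, or early termination for those who withdraw. Read literally, 12.5 includes Follow-Up and omits Day 109.
- SAP 6.11.4: screening, before Period 1, Day 109, early termination. Follow-Up is not named.

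**The case against.** The strongest reply is that this concerns the layout of a descriptive table. Protocol 17.6 promises by-treatment summaries only for laboratory tests and vital signs, and leaves other safety parameters to listings, so an overall ECG table already exceeds the protocol. All ECG data are listed, and SAP 6.3 sorts listings by sequence, so each subject's Period 3 treatment is identifiable. Pulse rate is summarised by treatment at the weekly visits under SAP 6.11.3. All of this stands, and it limits the point to the summary tables. It does not remove the point: pulse rate says nothing about PR or QTcF, a listing is not a summary, and SAP 6.11 and 6.11.4 still disagree.

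Readers might infer more than the documents support:

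- **That the table cannot show any TDS effect.** Step 3 shows dilution by about half, not absence.
- **That the SAP throws away a randomised comparison.** The data are kept and listed; they are just not tabulated that way.
- **That a split gives a clean comparison of TDS with Aricept.** The order of B and C is randomised, but the 24 h and 48 h gaps differ by design, every completer has had all three treatments, and the columns are imprecise.
- **That only the 5 mg TDS lacks a scheduled on-treatment ECG.** No treatment has one, since Day 109 follows the drug-free Day 108.
- **That early-termination ECGs are certainly merged with Day 109.** Only the table titles suggest it. Table 14.3.7.9 is by visit and may use separate rows, and SAP 6.2.3 points elsewhere.

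**Conclusion.** The point holds as one about the summary. SAP 6.11.4 conflicts with SAP 6.11, and the planned overall table cannot attribute an ECG change to the 10 mg TDS or to oral Aricept. A change confined to the TDS would show at about half size, or about 42% to 58% for splits from 20:28 to 28:20. The half rests on roughly equal allocation and dropout, which the documents do not state. The residual-exposure figures rest on the 70 h half-life and simple decay.

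The 5 mg TDS has no scheduled ECG at the end of its period, and re-tabulation cannot supply one. Neither the bioequivalence nor the adhesion conclusion is affected. The change is worth making because it is cheap and bears on the stated safety objective.

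**What to change.** - **Tables.** In SAP 6.11.4 and Tables 14.3.7.9 and 14.3.7.10, present Day 109 values, changes from the pre-Period 1 baseline, and shifts by treatment sequence, labelled with the Period 3 treatment (ABC = oral Aricept, ACB = 10 mg TDS). Keep the overall column as secondary. Name the baseline explicitly, because SAP 6.2.2 defines a period-specific baseline for by-treatment summaries and no ECG is scheduled before Period 3 dosing.
- **Footnote.** State the approximate gaps (24 h after patch removal in ACB, 48 h after the last tablet in ABC), and that the columns are descriptive and not a like-for-like comparison.
- **Early termination.** Show these ECGs separately by last treatment received, and reconcile SAP 6.2.3 with the two table titles.
- **Limits.** State that no ECG is scheduled at the end of Period 1 (5 mg TDS) or Period 2, and that the Day 109 ECG follows a drug-free day.
- **Reconciliation.** Align SAP 6.11 with 6.11.4. Align the Follow-Up or end-of-study ECG in Protocol 9.6 and 12.5 with the Schedule of Events and SAP 6.11.4, which do not include it, and clarify whether 12.5 is meant to cover Day 109.

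The cost is a few extra columns and some text, with no new data. The downsides are about 24 subjects per column and the unequal timing, which the footnote discloses.
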